*** Predicted risks**

Because both prostheses have proved their efficacy and safety by prospective pivotal trials

and many related studies, the predicted risks associated with the present study will be comparable to routinely performed aortic valve replacement.

If any adverse event or risk occurs, providing the standard management for them will be sufficient.

5) Criteria for suspension and dropout

Patients who decline to participate in the trial are suspended or drop-out

6) Safety

Safety outcomes will be a composite of death from any cause and individual major postoperative complications including low cardiac output, bleeding reoperation, perioperative myocardial infarction, perioperative stroke, acute kidney injury, respiratory complications, postoperative atrial fibrillation, and mediastinitis.

All safety outcome measures will be assessed and recorded at designated time intervals by research personnel at each individual center. Data regarding every event will be reviewed and adjudicated centrally by the principal investigator and sub-investigator.

7) Efficacy

Efficacy analysis will be performed for ITT(Intention to treat) group, and supplemental analysis will be performed for PP(Per protocol) and As treated group. The primary endpoint will be concluded as 'noninferior' if both ITT and PP analyses confirm the noninferiority.

ITT group includes all study population. PP group is constituted from the ITT group after excluding the patients with major violation of the study protocol.

The null hypothesis was that the Avalus™ was inferior to the CEPME based on the AVMPG at 1-year echocardiographic follow-up, with a non-inferiority margin of 3mmHg. The result for the primary endpoint was presented with 97.5% one-sided confidence interval for mean difference between groups. The non-inferiority test was performed using a t-test which compared mean difference between groups with the non-inferiority margin under the one-sided significance level of 0.025.

For analysis of 1-year clinical outcomes including all-cause mortality, cardiac death, and MAEs, events were counted at postoperative 1 year, and comparisons between the 2 groups were made using the chi-square test and Fisher's exact test. A P value of $< .050$ was considered statistically significant.

8) Schedules

- ① Study planning : October 1, 2018 – November 31, 2018
- ② Enrollment : January 1, 2019 (or after IRB approval) – June 30, 2022
- ③ Data analysis and reporting : January 1, 2022 – December 31, 2022

11. Data monitoring and Safety committee

1) Monitoring committee

[name] (Department of Thoracic and Cardiovascular Surgery, Seoul National University Hospital)
[name] (Department of Thoracic and Cardiovascular Surgery, Seoul National University Hospital)

2) Data and Safety Monitoring List

Operative mortality, low cardiac output, bleeding reoperation, perioperative myocardial infarction, perioperative stroke, acute kidney injury, respiratory complications, postoperative atrial fibrillation, and mediastinitis

3) Data and Safety Monitoring Periods

Safety outcomes will be monitored every 6 months.

4) Reporting drug adverse events, non-compliance, or unpredicted events

If any drug adverse event, non-compliance, or unpredicted event occurs, they must be reported within 15 working days from the date of recognition.

5) Withdrawal of the trial

If critical adverse events or complications associated with the trial occur and it is impossible to keep the trial going on, the trial will be withdrawn.

12. Ethics

The Investigators and all parties involved will conduct this study in adherence to the ethical principles based on Declaration of Helsinki, GCP, ICH guidelines and the applicable national and local laws and regulatory requirements. Relevant study documentation will be submitted to Ethics Committees of participating centers, according to local/national requirements, for review. Written

approval of the study must be obtained locally before the study commences at each participating center. Once protocol amendments or consent form modifications are approved and implemented at the lead center, updated documents will be provided to participating centers. On completion of the study, the regulatory authorities will be notified that the study has ended.

13. References

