**Prospective Randomized comparison Of prosthetic Valve Effective
orifice area: One-year analysis of two bovine PERIcardial valves
(PROVE-PERI trial)**

NCT 03796442

Trial Protocol v 1.4

Updated Dec 28, 2018

Protocol summary

Trial name and number	Prospective Randomized comparison Of prosthetic Valve Effective orifice area: One-year analysis of two bovine PERIcardial valves (PROVE-PERI trial) ClinicalTrial.gov 03796442
Objectives	This randomized controlled trial is designed to compare 1-year hemodynamic performances and clinical outcomes after aortic valve replacement (AVR) using a recently introduced and world-wide used bovine pericardial bioprostheses.
Design	Prospective randomized controlled trial
Study periods	IRB approval date ~ June 30, 2022
Subjects	Patients who are scheduled to undergo AVR
Sample size	Total 140 patients
Methods	Patients over 19 years of age who are scheduled to undergo AVR on a nonemergency basis and who are planned to undergo primary AVR using stented bioprostheses are assessed for eligibility for study enrollment. The exclusion criteria include (1) patients with concomitant mitral or tricuspid valve operation, (2) patients with infective endocarditis, (3) patients with severe left ventricular dysfunction (ejection fraction < 0.30), (4) patients with a medical history such as a malignant disease that might limit the possibility of mid-term follow-up and (5) patients who refuse study enrollment. Enrolled patients are randomly assigned to 1 of the 2 bioprostheses in a 1:1 manner. After surgery, early clinical and hemodynamic outcomes are evaluated following the protocol. After discharge, all patients undergo regular postoperative follow-up and are evaluated with echocardiography at 1-year follow-up.
Endpoints	The primary endpoint of the PROVE-PERI trial was mean pressure gradient across the aortic valve (AVMPG) on 1-year echocardiographic follow-up. The secondary endpoints were the effective orifice area (EOA) on 1-year echocardiographic follow-up and 1-year clinical outcomes including all-cause mortality, cardiac death and major adverse event (MAEs).
Safety	Postoperative complications including operative mortality, low cardiac output, bleeding reoperation, perioperative myocardial infarction, perioperative stroke, acute kidney injury, respiratory complications, postoperative atrial fibrillation, and mediastinitis were monitored for safety.

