Surgeries are performed under median sternotomy or upper partial sternotomy under cardiopulmonary bypass with cold cardioplegic arrest. After the diseased AV is excised, the annulus is prepared for landing the prosthesis, and the proper valve sizes for both types of

prostheses are decided before randomization. Then, randomization is performed with a web-based block randomization method with randomly determined block sizes of 4 and 6. After randomization, the assigned prosthesis is implanted with non-everting transverse mattress sutures. The knot-tying is performed manually or by using an automated knot-fastener.

Patients are evaluated with early clinical outcomes and early echocardiographic measurements. After discharge, all patients undergo regular postoperative follow-up through the outpatient clinic at 3- to 6-month intervals and are interviewed by telephone for confirmation of their condition if the last clinic visit has not been conducted as scheduled. At postoperative 1-year, clinical outcomes and echocardiographic measurements are evaluated as scheduled.

※ Randomization : Patients who meet the inclusion criteria and the exclusion criteria are randomly assigned to 1 of the 2 bioprostheses in a 1:1 manner. Randomization is performed with a web-based block randomization method (<https://mrcc.snuh.org/>) with randomly determined block sizes of 4 and 6, considering the institution as a stratification factor.

2) Outcome measures

- 1) Demographics: age, sex, height, weight, BMI, BSA, diagnosis, operation name
- 2) Preoperative data
 - Risk factors: DM, HTN, smoking, dyslipidemia, stroke, COPD, CKD, chronic liver disease, coronary disease, peripheral vascular disease, history of cardiac surgery, New York Heart Association functional class, STS mortality risk, EuroSCORE II
 - Echocardiographic measurements: Effective orifice area, mean pressure gradient, peak pressure gradient, LA dimension, LV ejection fraction, LV end diastolic dimension, LV end systolic dimension, pulmonary artery systolic pressure, TR severity, etc.
 - Electrocardiography
 - Laboratory tests: CBC, routine chemistry, NT-proBNP, CRP, ABGA, lactate, PT, aPTT
 - CT scan (thoracoabdominal CT angio)
 - Pulmonary function test
- 3) Operative data: CPB time, ACC time, concomitant procedures, operative findings
- 4) Postoperative data

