 - Early clinical outcomes: op mortality, op morbidities (low cardiac output, bleeding reoperation, perioperative myocardial infarction, perioperative stroke, acute kidney injury, respiratory complications, postoperative atrial fibrillation, and mediastinitis)

- Echocardiographic measurements: Effective orifice area, mean pressure gradient, peak pressure gradient, LA dimension, LV ejection fraction, LV end diastolic dimension, LV end systolic dimension, pulmonary artery systolic pressure, TR severity, etc.
- Electrocardiography: 1st, 2nd and 3rd AV block, bundle branch block

5) 1-year follow-up data

- Clinical outcomes: all-cause mortality, cardiac death and major adverse events (valve-related mortality, structural valve deterioration, nonstructural dysfunction, thromboembolic and bleeding events, prosthetic valve endocarditis, AV reintervention or the need for a new permanent pacemaker or defibrillator within 14 days after the index operation), last follow-up date, New York Heart Association functional class
- Echocardiographic measurements: Effective orifice area, mean pressure gradient, peak pressure gradient, LA dimension, LV ejection fraction, LV end diastolic dimension, LV end systolic dimension, pulmonary artery systolic pressure, TR severity, etc.
- Electrocardiography: 1st, 2nd and 3rd AV block, bundle branch block

※ Primary clinical endpoint

mean pressure gradient across the aortic valve (AVMPG) on 1-year echocardiographic follow-up

※ Secondary clinical endpoint

the effective orifice area (EOA) on 1-year echocardiographic follow-up

operative mortality, operative morbidities

1-year clinical outcomes (all-cause mortality, cardiac death and major adverse events)

3) Differences from previous treatments and studies

When compared with previous treatments, the operative strategies and perioperative management are identical, but only the bioprostheses used in the treatments are different.

When compared with previous studies, all studies previously performed were prospective single-arm designs or retrospective studies. To the best of our knowledge, the present study is the first prospective randomized controlled trial comparing results of AVR using the Avaluus™ valve with those using another bovine pericardial valve that has been used worldwide.

4) Risks associated with the study

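### Events are adjudicated by the trial's own investigators and no masking to valve type is described, so judgement-based secondary outcomes could be classified differently by arm

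*Protocol*

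**What the plan says.** Protocol Section 10, 6) Safety sets out two steps. First: "All safety outcome measures will be assessed and recorded at designated time intervals by research personnel at each individual center". Then: "Data regarding every event will be reviewed and adjudicated centrally by the principal investigator and sub-investigator". The same section defines what is being assessed: "Safety outcomes will be a composite of death from any cause and individual major postoperative complications including low cardiac output, bleeding reoperation", followed by further named complications.

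The 1-year clinical outcomes are listed elsewhere, in Section 10, 2) Outcome measures. They are all-cause mortality, cardiac death and major adverse events. The components of the last include "valve-related mortality, structural valve deterioration, nonstructural dysfunction, thromboembolic and bleeding events, prosthetic valve endocarditis", together with reintervention on the aortic valve and early need for a pacemaker or defibrillator. Only event names are given there, not definitions.

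On when the valve becomes known, Section 10, 1) says: "After randomization, the assigned prosthesis is implanted with non-everting transverse mattress sutures". On design, the protocol summary says only: "Prospective randomized controlled trial". Neither document, in the text available, mentions masking of adjudicators, a rule for standing aside, or an independent events committee.

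Operative morbidities, cardiac death and major adverse events are secondary endpoints in Protocol Section 10, 2) and in the SAP. The SAP compares them between arms by chi-square and Fisher's exact test, with significance at P < .050.

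**The concern.** The valve is assigned and implanted in the operating room, so the operating team knows it, and it would ordinarily appear in the operative record. The people who classify events are trial investigators, and nothing in the available text provides for withholding the valve from them.

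That matters little for events that leave no room for opinion. It matters more where someone must decide whether a death was cardiac, whether a postoperative state amounts to low cardiac output, or whether a respiratory problem is a complication. With no written definitions, the room for judgement is wider. If knowledge of the valve tilts these decisions, the between-arm comparison of secondary outcomes is distorted. The distortion could create a difference or hide one. The protocol's background states that comparing safety, as well as efficacy, is a purpose of the trial.

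**Working it through.** **1. What the text settles.**

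| Question | Where | Answer |
|---|---|---|
| Who records safety outcomes? | Protocol 10, 6) | Research personnel at each center |
| Who classifies? | Protocol 10, 6) | Principal investigator and sub-investigator, centrally |
| Are they masked to valve? | Both documents | Not described |
| Did they operate on trial patients? | Both documents | Not stated |
| Does the rule reach the 1-year valve events? | Protocol 10, 6) against 10, 2) | Unclear: the wording is broad, but it sits under Safety, whose list is death and postoperative complications |
| Are events defined? | Both documents | Names only |

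On the broad reading, the 1-year events are adjudicated with no masking described. On the narrow reading, no adjudication is described for them at all. Either way the section needs amending.

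**2. Which outcomes are exposed.**
- Exposed: low cardiac output, respiratory complications, cardiac death and, on the broad reading, valve-related mortality, structural deterioration and nonstructural dysfunction.
- Little exposed: reintervention, and new pacemaker or defibrillator.
- Not exposed: all-cause mortality, and the primary endpoint (mean gradient), which is measured by echocardiography and is not an adjudicated event.

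**3. The denominator.** The plan gives no figure for event rates, but it does give the number per arm. Inputs from Protocol Section 9, 3): SD 4.3 in both arms, means 12.6 and 11.9, margin 3, one-sided alpha 0.025, power 80%.

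n = (1.960 + 0.842)² × (4.3² + 4.3²) / (0.7 − 3)² = 54.87, so 55. With the t distribution, power is 79.4% at 55 and 80.1% at 56, which gives the plan's 56. Then 56 / (1 − 0.20) = 70 per arm. The plan's figure reproduces.

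**4. Illustration with assumed event risks.** Take a risk of 10% (range 5% to 15%).
- Expected events per arm: 70 × 0.10 = 7 (70 × 0.05 = 3.5 to 70 × 0.15 = 10.5, so about 4 to 11).
- Reclassifying two events in one arm: 2/70 = 2.9 percentage points. For example 7/70 = 10.0% becomes 5/70 = 7.1%.
- Testing 7/70 against 5/70: Fisher P = 0.76, chi-square P = 0.55. At the ends of the range, 4 against 2 gives Fisher P = 0.68, and 11 against 9 gives 0.81.

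On its own, then, a shift of two events does not produce a significant difference.

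**5. Effect on the false-positive probability.** Assume equal true risks, 70 per arm, and a share of one arm's events not counted. Summing the exact binomial probabilities over all tables with P < .05 gives:

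| True risk | Share not counted | False difference | Fisher | Chi-square |
|---|---|---|---|---|
| 5% | 0 | 0 | 1.4% | 4.8% |
| 5% | 20% to 40% | 1 to 2 points | 1.5% to 2.4% | 5.5% to 8.3% |
| 10% | 0 | 0 | 2.5% | 5.1% |
| 10% | 20% to 40% | 2 to 4 points | 3.6% to 7.6% | 7.1% to 14.2% |
| 20% | 0 | 0 | 3.1% | 5.1% |
| 20% | 20% to 40% | 4 to 8 points | 6.4% to 19.0% | 9.4% to 25.1% |

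The effect is small at 5% and grows with the event risk. Both the risks and the shares are assumptions.

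**The case against.** The strongest reply is that the documents are silent on masking. They do not say that review is open, and part of the protocol is not available to us. A reader might infer that the adjudicators know the valve, or that they judge patients they operated on. The documents state neither, and the point should not be put that way.

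A reader might also infer that every valve event falls under this rule. The sentence stands under Safety, and the lists in the protocol summary and in Section 11 likewise cover operative death and postoperative complications only. The reach of the rule is therefore uncertain, and this objection stands.

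It is also fair to say that central review by two people is already specified, that the only non-inferiority hypothesis concerns the gradient, that no margin is set for safety, and that the two-event example changes no test result. All of that limits the importance of the point.

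It does not remove it. Secondary outcomes that depend on judgement are compared between arms, and the plan already separates recording from classification. Redaction between those two steps is less open to bias than the procedure as written, and it needs no new assessor.

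**Conclusion.** The point holds in a limited form. The plan names the trial's own investigators as adjudicators and describes no masking to valve type, so judgement-based secondary outcomes could be classified differently by arm. Whether the 1-year valve events are included depends on how broadly the rule is read.

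The documents do not support a claim that bias has occurred or favours one valve, nor a claim that the primary conclusion is at risk. The size and direction of any bias cannot be derived from them. The 2.9-point shift and the false-positive figures rest wholly on assumed event risks and assumed misclassification. This is a cheap improvement worth making. It is not an error in the plan's figures, and no planned number changes.

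**What to change.** Amend Protocol Section 10, 6) as follows, and carry the definitions into the SAP.

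- **Scope.** State that adjudication covers the 1-year cardiac deaths and the components of major adverse events, as well as the postoperative complications.
- **Redaction.** Center research personnel remove valve name, model, size and other identifying operative details from each event packet.
- **Definitions.** Add a definition for each event, fixed in advance, since Section 10, 2) gives names only.
- **Order.** The same two adjudicators classify each event before allocation is merged with the event data.
- **Standing aside.** Where possible, an adjudicator who operated on the patient leaves the classification to the other. If both operated, they classify from the redacted packet and the event is flagged.
- **Reporting.** Report events that rest on valve imaging or explant as incompletely masked.

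The cost is a short amendment, the writing of definitions and some redaction work. No additional patients or committee are needed. The main limitation is that masking will be weakest for structural deterioration, nonstructural dysfunction and reintervention, where imaging or explant findings may reveal the valve.

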The study is designed to have 80% power to detect 1-year AVMPG of 12.6 ± 4.3 mmHg for the study prosthesis [2] and 11.9 ± 4.3 mmHg for the control prosthesis, [3-5] with a 1-sided type I error of 2.5% and a noninferiority margin of 3 mmHg. The noninferiority margin is determined by the values of 15 mmHg for AVMPG of clinically significant aortic stenosis [6] and 12 mmHg for AVMPG of the control prosthesis. Fifty-six patients in each group are needed to complete the study cohort. Allowing for a 20% dropout rate during the 1-year follow-up, we determine that the recruitment of 70 patients in each group is necessary.

- (1) Level of significance (α) = 0.025
- (2) Type II error (β) = 0.20, power of the test = 80%
- (3) Drop out rate = 20%
- (4) One-tailed test

H_0 (null hypothesis): $\mu_1 - \mu_2 \geq \delta$

H_1 (alternative hypothesis): $\mu_1 - \mu_2 < \delta$

(μ_1 : mean AVMPG of the study group on 1 – year echocardiographic follow – up ,

μ_2 : mean AVMPG of the control group on 1 – year echocardiographic follow – up

δ : noninferiority margin)

The calculation was performed using PASS Software(Power Analysis and sample size software: <http://www.ncss.com>), and the calculated formula is as follows.

$$n = \frac{(Z_\alpha + Z_\beta)^2 (\sigma_1^2 + \sigma_2^2)}{((\mu_1 - \mu_2) - \delta)^2}$$

μ_1 = mean AVMPG of the study group on 1 – year echocardiographic follow – up

μ_2 = mean AVMPG of the control group on 1 – year echocardiographic follow – up

σ_1 = standard deviation of AVMPG of the study group on 1 – year echocardiographic follow – up

σ_2 = standard deviation of AVMPG of the control group on 1 – year echocardiographic follow – up

δ : noninferiority margin

4) Subject recruitment plan

Subject recruitment will be performed for the patients who are scheduled to undergo AVR and who are hospitalized at Seoul National University Hospital and Seoul National University Bundang Hospital after providing sufficient explanation and informed consents. The subjects will be recruited competitively.

10. Methods

1) Detailed process of the study

Patients over 19 years of age who are scheduled to undergo AVR on a nonemergency basis and who are planned to undergo primary AVR using stented bioprostheses at 2 institutions are assessed for eligibility for study enrollment. After excluding the patients who meet the exclusion criteria and who refuse to participate, enrolled patients are randomly assigned to 1 of the 2 bioprostheses in a 1:1 manner.

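### The protocol's stated dates do not fit its 1-year primary endpoint: enrolment is listed as open until the day the study period ends, and reporting closes six months later

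*Protocol*

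**What the plan says.** Three places in the protocol give calendar dates.

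- Protocol summary, Study periods: "IRB approval date ~ June 30, 2022".
- Section 10, item 8 (Schedules), second line: "Enrollment : January 1, 2019 (or after IRB approval) – June 30, 2022".
- Section 10, item 8, third line: "Data analysis and reporting : January 1, 2022 – December 31, 2022".

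The primary endpoint in Section 10, item 2 is "mean pressure gradient across the aortic valve (AVMPG) on 1-year echocardiographic follow-up". The Protocol summary (Methods) applies that assessment to everyone: "After discharge, all patients undergo regular postoperative follow-up and are evaluated with echocardiography at 1-year follow-up". Section 10, item 1 repeats it: "At postoperative 1-year, clinical outcomes and echocardiographic measurements are evaluated as scheduled". The same item places randomization inside the operation: "After randomization, the assigned prosthesis is implanted with non-everting transverse mattress sutures". One year after surgery is therefore also one year after randomization.

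The schedule has no follow-up line. The SAP gives no calendar schedule. In the text reviewed, which lacks some early protocol pages, neither document states a last-enrolment date separate from the line above, a data cut-off or a rule for database lock.

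**The concern.** An endpoint measured at one year needs at least a year between the last operation and the end of data collection. Here that gap is zero for the study period and six months for reporting. The schedule cannot be followed as printed if anyone is enrolled late in the listed window.

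Two things are at stake. If follow-up simply continues, part of the primary-endpoint data would be collected after the study period stated in the protocol, and the reporting date would be missed. If someone instead treated the printed dates as a data cut, late enrollees would lack the primary endpoint for an administrative reason. The sample-size section does not provide for that, because its allowance is for loss during follow-up: "Allowing for a 20% dropout rate during the 1-year follow-up".

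**Working it through.** **1. The plan's own sample size, to show that it is not in question.** Inputs from Protocol Section 9, item 3: SD 4.3 mmHg in both groups, assumed difference 12.6 − 11.9 = 0.7 mmHg, margin 3 mmHg, one-sided alpha 0.025, power 80%.

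- Printed formula: n = (1.960 + 0.842)² × (4.3² + 4.3²) / (0.7 − 3)² = 7.85 × 36.98 / 5.29 = 54.9, so 55 per group.
- Noncentral t: power is 79.4% at 55 and 80.1% at 56 per group, which gives the stated 56.
- Dropout: 56 / 0.80 = 70 per group, 140 in total, as stated.

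**2. Last possible echocardiogram.** Last enrolment June 30, 2022 plus 1 year = June 30, 2023.

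- Against the study end, June 30, 2022: 365 days late.
- Against the reporting end, December 31, 2022: 181 days late.

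**3. Latest enrolment date that still fits each printed date** (printed date minus 1 year).

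| Printed date | Latest enrolment |
|---|---|
| Study period ends June 30, 2022 | June 30, 2021 |
| Reporting ends December 31, 2022 | December 31, 2021, with no time left for analysis |

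A visit window would move these cut-offs only by its own width, and the visible text gives none. The proviso about IRB approval can move only the start of enrolment, not its end.

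**4. The alternative reading, in which the enrolment line covers enrolment plus follow-up.** The last-enrolment date is then unstated. If it is June 30, 2021 or earlier, every echocardiogram falls inside the study period. Analysis is listed as opening on January 1, 2022. It opens after the last 1-year echocardiogram only if enrolment closes by December 31, 2020.

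**5. How many patients could be involved.** The documents give no accrual rate. As an illustration only, assume 140 patients accrue uniformly over the full 42 months from January 1, 2019 to June 30, 2022, which is 140 / 42 = 3.33 per month.

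- Enrolled in the last 12 months, echocardiogram due after the study period: 12 × 3.33 = 40 of 140 (28.6%).
- Enrolled in the last 6 months, echocardiogram due after reporting ends: 6 × 3.33 = 20 of 140 (14.3%).

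If accrual finished by June 30, 2021, both counts would be zero.

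**The case against.** The best defence is that the line was meant to cover enrolment and follow-up together. It ends on the day the study period ends, the list has no follow-up line, and analysis opens six months before the line closes. On that reading no echocardiogram need fall outside the dates. The target is also a fixed 140 patients, so accrual could finish well before the window closes. Or the date may be a slip: the study-planning line in the same list ends on November 31, 2018, which does not exist.

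All of this is plausible, and it limits what can be claimed about consequences. It does not remove the inconsistency. The line is labelled enrolment, and nothing visible says that it includes follow-up. If it does, the last-enrolment date is missing. Either way the text needs correcting, and the documents do not show which date is mistaken.

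A reader might go further and infer that the trial will be underpowered. With the uniform accrual assumed above, a data cut at June 30, 2022 would leave 50 per group (75.4% power), or 40 after 20% dropout (65.6%). A cut at December 31, 2022 would leave 60 per group (82.8%), or 48 after dropout (73.7%). These figures do not measure this defect. They need both an accrual pattern and a calendar data cut, and neither document states either. The text points the other way. Every patient is to have the 1-year echocardiogram, the intention-to-treat group in Section 10, item 7 is the whole study population, and the SAP compares all outcomes on that basis.

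Nor is an analysis start of January 1, 2022 a contradiction in itself, since whether it precedes the last echocardiogram depends on when enrolment closes.

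**Conclusion.** The point holds as an internal inconsistency of dates. Read literally, the protocol cannot enrol to June 30, 2022, give every patient a 1-year echocardiogram, and end the study period on June 30, 2022 and reporting on December 31, 2022. The mismatch is up to 365 days for the study period and up to 181 days for reporting. This follows from the printed dates alone. The patient counts do not: they rest on the assumed uniform accrual.

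The sample size, margin, endpoint and test stand. No power is lost if follow-up runs to completion or if accrual ends early enough, so any power loss is hypothetical. That the dates need reconciling is firm; which of them is wrong cannot be determined from the documents. The correction is small but should be made.

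**What to change.** The investigators should state which date was intended and reconcile the Protocol summary with Section 10, item 8 in one of two ways.

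- **(a) Keep enrolment open to June 30, 2022.** Extend the study period to at least June 30, 2023 plus any visit window, with reporting after that.
- **(b) State an earlier last-enrolment date.** It should lie at least 1 year plus any visit window before the study period ends. If the study period still ends June 30, 2022, that means June 30, 2021 less the window.

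In either case, align the start of the primary analysis with the last 1-year echocardiogram. State in both protocol and SAP that database lock and the primary analysis follow the last enrolled patient's 1-year echocardiogram. Separate schedule lines for last enrolment and last 1-year echocardiogram would prevent a recurrence, and the impossible November date can be corrected in the same amendment.

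The cost is a date amendment with IRB approval and no extra patients. Under (a), reporting ends at least 6 months later than now stated. Under (b), recruitment must be faster only if accrual had been planned over the full 42 months. Assuming uniform accrual from January 1, 2019 and closing on June 30, 2021, it would be 140 / 30 = 4.67 per month against 140 / 42 = 3.33. If the 42 months already included the follow-up year, nothing needs to speed up.
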